4.7.1.1 Handling of Dropouts or Missing Data

Patients with missing efficacy data or indeterminate outcomes will be considered as treatment failures for efficacy analyses.

For the primary endpoint, patients who discontinued for lack of efficacy or rescue medication use will be considered as treatment failure.

Patients who take rescue medication, discontinue or are lost to follow up, and for whom the pain persists at the time of the last observation, will be censored at maximum length (Day 17) in those cases when the diary information is not available.

To explore the effect of the handling of the missing data and assess the robustness of the efficacy results, a complete case analysis will be carried out (i.e. all efficacy analyses will be repeated on actual values i.e. without imputation of the missing data) as sensitivity analysis on the MITT population.

4.7.1.2 Multiple Comparisons/Multiplicity

No adjustment for multiple comparisons is planned for the efficacy endpoints being monitored.

Safety results, including the summaries of AEs and changes in vital signs data, will be interpreted on clinical grounds. No formal statistical hypothesis testing will be performed.

4.7.1.3 Interim Analyses

No interim analyses are planned.

4.7.1.4 Examination of Subgroups

To assess the effects of various demographic and baseline characteristics on treatment outcome, subgroup analyses for the primary endpoint, therapeutic outcome at Visit 3, and the principal secondary endpoint, TEOP, will be performed based on the following subgroups:

- Age Group

- 6 months to <18 years, \geq 18 years
- 6 months to <7 years, 7 years to <13, \geq 13 years
- 6 months to <12 years, 12 years to <18 years, \geq 18 years
- Ear wick placement: yes, no

Descriptive summaries and analyses will be provided for each endpoint by treatment group and subgroup for the MITT and MITT-PA/SA populations.

For the primary endpoint, the Cochran-Mantel-Haenszel (CMH) test will be used, stratifying on subgroup. Differences in response rates with the corresponding 95% CIs will be reported for each subgroup level. The proportions for each subgroup level will be shown with the p-value from the Breslow Day test for homogeneity of the odds ratios.

For the principal secondary endpoint, each age subgroup comparison will be made using a Cox proportional hazards model with factors for treatment group, age group, and the age group-by-treatment interaction. For the ear wick placement subgroup, the comparison will be made using a Cox proportional hazards model stratified on age (6 months to <18 years versus \geq 18 years) with factors for treatment group, ear wick placement, and the ear wick placement-by-treatment interaction. The estimated hazard ratios together with their associated 95% CI and two-sided p-value will be shown for each subgroup.

Subgroup analyses may also be performed based on concomitant medication type if necessary as outlined in Section 4.5.3.

4.7.2 Primary Efficacy Variable – *Therapeutic Response*

The primary endpoint for the assessment of efficacy is therapeutic response at Visit 3 in the MITT-PA/SA population. Efficacy analyses of the primary endpoint will also be conducted on the MITT, MPP CITT and CPP populations.

Therapeutic cure is the combined clinical and microbiological cure. Clinical and microbiological cure will be considered achieved if edema, otalgia, and otorrhea are resolved with no further requirement of antimicrobiological therapy and bacteriological response is Eradication or Presumed Eradication.

Overall Clinical Outcome is based on the Total Signs/Symptoms Scale (TSSS), which is calculated by the sum of otalgia score + edema score + otorrhea score. Clinical cure is a TSSS equal to 0.

Otalgia is the level of pain in the ear and is measured on a scale of 0 to 3. It will be assessed as:

- Severe (3) if it interferes with activities of daily living;
- Moderate (2) if it causes discomfort but does not interfere with activities of daily living;
- Mild (1) if there is awareness of pain but not much discomfort

- Absent (0) if there is total absence of pain.

Edema is the level of swelling in the ear and is measured on a scale of 0 to 3. It will be assessed as:

- Severe (3) if the tympanic membrane is not visible because of swelling;
- Moderate (2) if the tympanic membrane is partially visible;
- Mild (1) if there is some swelling but the tympanic membrane is fully visible;
- Absent (0) if there is no visible swelling.

Otorrhea is the discharge from the ear and is measured on a scale of 0 to 3. It will be assessed as:

- Severe (3),
- Moderate (2),
- Mild (1),
- Absent (0).

Bacteriological response will be categorized for each patient based on the microbiological culture results. Positive results will be categorized into three groups: target pathogen, non-target pathogen, and non-pathogen. For analysis purposes, patients with a target pathogen or non-target pathogen will be considered to be culture positive for a pathogen. Negative results and non-pathogen positive results will be considered to be culture negative for a pathogen. For any patient with a culture positive for a pathogen at Visit 1, bacteriologic response at Visits 3 will be classified as:

- Eradication if the culture does not show growth of any pathogen;
- Presumed Eradication if there is no material to culture and the Overall Clinical Outcome is Clinical Improvement or Clinical Cure as defined above;
- Persistence if any pathogen cultured at Visit 1 is still present;
- Presumed Persistence if the Overall Clinical Outcome is Clinical Failure but no culture result is available from Visit 3;
- Superinfection if a pathogen not present at Visit 1 is now present (presence of a nonpathogenic organism will not be considered Superinfection); or
- Indeterminate if none of the above definitions are met and the bacteriologic response cannot be determined.

For any patient with a culture positive for a pathogen at Visit 1, bacteriologic response at Visits 4 will be classified as:

- Eradication if the culture does not show growth of any pathogen;
- Presumed Eradication if there is no material to culture and the Overall Clinical Outcome is Clinical Improvement or Clinical Cure as above;
- Persistence if any pathogen cultured at Visit 1 is still present;
- Presumed Persistence if the Overall Clinical Outcome is Clinical Failure but no culture result is available from Visit 4;

- Recurrence if there is reappearance of the pathogen eradicated or presumably eradicated at Visit 3;
- Superinfection if a pathogen not present at Visit 1 and Visit 3 is now present (presence of a nonpathogenic organism will not be considered Superinfection);
- Reinfestation if there is isolation of a new pathogen different from the one eradicated or presumably eradicated at Visit 3; or
- Indeterminate if none of the above definitions are met and the bacteriologic response cannot be determined.

For any patient with a negative culture or a culture positive for a non-pathogen at Visit 1, bacteriologic response at Visits 3 will be classified as:

- Presumed Eradication if the culture does not show growth of any pathogen or if there is no material to culture and the Overall Clinical Outcome is Clinical Improvement or Clinical Cure as defined above;
- Presumed Persistence if the Overall Clinical Outcome is Clinical Failure but no culture result is available from Visit 3;
- Superinfection if a pathogen not present at Visit 1 is now present; or
- Indeterminate if none of the above definitions are met and the bacteriologic response cannot be determined.

For any patient with a negative culture or a culture positive for a non-pathogen at Visit 1, bacteriologic response at Visits 4 will be classified as:

- Presumed Eradication if the culture does not show growth of any pathogen or if there is no material to culture and the Overall Clinical Outcome is Clinical Improvement or Clinical Cure as defined above;
- Presumed Persistence if the Overall Clinical Outcome is Clinical Failure but no culture result is available from Visit 4;
- Recurrence if there is no material to culture, the Overall Clinical Outcome is Clinical Failure, and the Overall Clinical Outcome at Visit 3 is Clinical Cure;
- Superinfection if a pathogen not present at Visit 1 and Visit 3 is now present;
- Indeterminate if none of the above definitions are met and the bacteriologic response cannot be determined.

The above rules will be used for microbiological outcome summaries for the patients in the CITT and CPP populations that have no pathogen at Visit 1, since microbiological response cannot be calculated without any pathogen at Visit 1.

If Overall Clinical Outcome at Visit 3 is Clinical Failure (whether or not the patient discontinues prematurely) and no bacterial culture is performed at Visit 3, the bacteriologic response at Visit 3 will be Presumed Persistence. If Overall Clinical Outcome at Visit 4 is Clinical Failure and no bacterial culture is performed at Visit 4, the bacteriologic response at Visit 4 will be Presumed Persistence.

Therapeutic cure: TSSS (otalgia+edema+otorrhea) of 0 and bacteriological response of eradication or presumed eradication

Therapeutic failure:

- Positive culture for pathogens (independent of TSSS) or
- Negative culture or presumed eradication with TSSS>0

If a patient took rescue medication prior to Visit 3, the response will be considered a failure at Visit 3. Similarly, if patient took rescue medication prior to Visit 4, the response will be considered a failure at Visit 4.

Therapeutic response will be summarized by treatment group and visit in terms of proportion of cures and failures at each visit.

A Pearson's Chi Squared test for independence will be used to test the hypotheses states in Section 4.7.1 that there is no difference between the combined treatment and each individual component at Visits 3 and 4. If less than 80% of the expected counts are less than 5 or at least one category has no patients in a treatment group, then Fisher's exact test will be used. Differences in response rates with the corresponding 95% CIs will be reported. Sensitivity analyses to investigate the impact of the choice of method for handling missing data and the choice of analysis population will be performed as described in Section 4.7.1.3.

The homogeneity of the treatment effect for a number of important subgroups will be investigated as described in Section 4.7.1.4.

A by-patient listing of the therapeutic response will be provided.

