## 5.5 Patient Identification and Randomization

Patients will be randomized at Visit 1, after signing informed consent (and assent form, when applicable) and meeting eligibility criteria. A block randomization procedure will be conducted through an Interactive Web Response System (IWRS) which will assign a patient number, which will be used to identify the patient during screening and, if applicable, throughout the duration of the study. Patients who do not meet the inclusion and exclusion criteria will be registered as screen failures through the IWRS.

For patients who have bilateral otitis externa, one ear will be considered the evaluable ear, and it will be randomized to a treatment group. If one ear has a higher total symptom score (as defined in Section Overall Clinical Outcome7.1.1.5) than the other, the ear with the higher score will be the evaluable one. If the symptom score is identical in both ears, the investigator will select the evaluable ear. In either case, the non-evaluable ear will receive the same treatment as the evaluable ear.

Patients will be stratified at enrollment by age group. Age will be classified into 2 groups:

- Younger than 18 years old, and
- 18 years old and older.

It is planned that the total number of patients in the study will be evenly divided between the 2 age groups. Stratification is being performed to ensure adequate representation of each age group in the study and not for statistical considerations.

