##### ***10.1.10.1 Primary efficacy endpoint***

###### ***Primary analysis of the primary endpoint***

The primary efficacy endpoint will be the therapeutic cure at Visit 3 in the MITT-PA/SA population.

In order for the requirements of the combination policy to be satisfied, both comparisons of the combination to the components alone must show the combination to be statistically significantly better than the component alone using a two-sided 0.05 significance level.

The number and percentage of patients with therapeutic cure at Visit 3 will be summarized by treatment group. The proportion of patients with a therapeutic cure will be compared between the treatment groups by using a chi-squared test.

Efficacy analyses of the primary endpoint will also be conducted on the MITT, MPP, CITT and CPP populations.

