4.7 Efficacy Evaluation

4.7.1 Hypothesis

This study is designed to test for superiority. The primary analyses will compare the combination treatment group with each component alone using the MITT-PA/SA population. The null hypotheses will be that there is no difference between Ciprofloxacin plus Fluocinolone acetonide and Ciprofloxacin alone and that there is no difference between Ciprofloxacin plus Fluocinolone acetonide and Fluocinolone acetonide alone. The alternative hypothesis will be that there is a difference. Symbolically, this is expressed as follows:

$$H_0: p_{\text{Ciprofloxaci plus Fluocinolone acetonide}} = p_{\text{Ciprofloxacin}}$$
$$H_a: p_{\text{Ciprofloxaci plus Fluocinolone acetonide}} \neq p_{\text{Ciprofloxacin}}$$

and

$$H_0: p_{\text{Ciprofloxaci plus Fluocinolone acetonide}} = p_{\text{Fluocinolone acetonide}}$$
$$H_a: p_{\text{Ciprofloxaci plus Fluocinolone acetonide}} \neq p_{\text{Fluocinolone acetonide}}$$

where p is the proportion of patients with therapeutic cure.

A two-sided chi-square (or χ^2) test with $\alpha=0.05$ will be used to test this hypothesis and conduct the between-treatment comparison. This approach will also be used for other (secondary) efficacy endpoints as described in Section 2.

The principal secondary analysis will also compare the combination treatment group with each component alone. The null hypothesis is that there is no difference in time to end of pain between the combination and the components alone. The alternative hypothesis is that there is difference in time to end of pain between the combination and the components alone.

The comparison will be made using the log-rank test stratified on age (6 months to <18 years versus ≥ 18 years) with $\alpha=0.05$.

Effective Date: [REDACTED]
Related to: [REDACTED]

CONFIDENTIAL

Project Document Version No. 2.0
Project Document Effective Date: Date of last signature
Page 16 of 34

Only assessments in the evaluable ear will be used for efficacy analyses.

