4.10 Determination of Sample Size

Planned enrollment is 500 children, adolescents and adults. Patients will be stratified at enrollment so that approximately 50% of those enrolled will be younger than 18 years old and approximately 50% will be over 18 years old or older. Stratification is being performed to ensure adequate representation of each age group in the study and not for statistical considerations.

We have not been able to find an accurate estimation of study's main variable (therapeutic cure) in previous investigations with Ciprofloxacin 0.3% otic solutions in the treatment of AOE. Rates of patients cured, with different definitions from ours, have been estimated within a range between 60% and 70%. Moreover, in two comparative trials testing the same combination (same product) versus Ciprofloxacin alone in the treatment of AOMT, the percentage of therapeutic cure in patients with *Pseudomonas aeruginosa* and *Staphylococcus aureus* was around 50%.

For the calculation of the sample size for this study, the assumption is made that the Ciprofloxacin alone group will have a therapeutic cure rate of 62%, and that the combination will increase it by a relative 25%, which would represent a therapeutic cure rate of 78%. Assuming a two-sided significance level of 5%, and a statistical power of 80%, the required number of patients in each group would be 150. The randomization schedule is defined as 2:2:1 (Ciprofloxacin plus Fluocinolone

acetonide:Ciprofloxacin:Fluocinolone acetonide), so the total number of evaluable patients to be recruited is 375 (150 : 150 : 75). It is expected that approximately 80% of enrolled patients will complete the study.

In this study, evaluable patients are those with a positive pathogen microbiological culture at baseline (MITT population). From previous studies in AOE, the rate of patients included with a negative culture at baseline is approximately 25%, and therefore the number of patients to be finally recruited to obtain 375 evaluable patients would be 500.

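### A cheap gain, not an error: the valid but unstratified chi-squared on the primary endpoint could be replaced by the age-stratified Cochran-Mantel-Haenszel test the SAP already plans

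*SAP*

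**What the plan says.** - **Primary test.** SAP 4.7.2: a Pearson "Chi Squared test for independence will be used to test the hypotheses states in Section 4.7.1". SAP 4.7.1 specifies the same two-sided test at 0.05. Protocol 10.1.10.1: "The proportion of patients with a therapeutic cure will be compared between the treatment groups by using a chi-squared test". None of the three mentions age.
- **Enrolment.** Protocol 5.5: "Patients will be stratified at enrollment by age group", the groups being under 18 and 18 and over. SAP 4.10 gives the purpose: "Stratification is being performed to ensure adequate representation of each age group in the study and not for statistical considerations". Protocol 5.5 specifies block randomisation through the IWRS but does not say whether the blocks run within age group.
- **Confirmatory pain endpoint.** SAP 4.7.1: "The comparison will be made using the log-rank test stratified on age", with the same two groups.
- **Age-stratified analysis of cure.** SAP 4.7.1.4 plans a CMH test of the primary endpoint by subgroup, including under 18 versus 18 and over, but only as a subgroup analysis.
- **Protocol synopsis, Statistical Methods.** It names an age-stratified log rank test for therapeutic cure, which agrees with neither the protocol body nor the SAP.

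**The concern.** Age group is known for every patient, is used to stratify enrolment, and is used in one of the two confirmatory analyses but not in the one that decides the trial. If age predicts cure, an unstratified comparison counts between-age variation as noise. A stratified test removes it and has somewhat more power. If the arms are also balanced within age by design, the unstratified variance is too large and the test becomes conservative.

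Both component comparisons must succeed. The plan gives no assumed cure rate for fluocinolone alone (75 evaluable patients), so that comparison has no documented power margin.

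**Working it through.** **1. The plan's own figure.** SAP 4.10: "Assuming a two-sided significance level of 5%, and a statistical power of 80%, the required number of patients in each group would be 150". The inputs are 62% for ciprofloxacin and a relative increase of 25%: 0.62 × 1.25 = 0.775, printed as 78%. The pooled two-proportion formula is

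n = [1.96·√(2p̄q̄) + 0.8416·√(p₁q₁ + p₂q₂)]² / (p₂ − p₁)²

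At 62% versus 77.5%, p̄ = 0.6975, and n = (1.2732 + 0.5389)² / 0.155² = 136.7, so 137. With continuity correction this becomes 150, as stated. At the printed 78% the formula gives 128 without correction and 140 with it.

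**2. Power of the planned chi-squared at 150 versus 150.** At 62% versus 78%, (0.16·√150 − 1.96·√0.42) / √0.4072 = (1.960 − 1.270) / 0.638 = 1.08, so power is 86.0%. At 77.5% it is 83.6%.

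**3. Size of the chi-squared if arms are balanced within age.** Take a common cure rate p = 0.62, a 50:50 age split, and a cure gap d between age groups. The documents give no cure rate by age, so d is an assumption and a range is shown.

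size = 2·[1 − Φ(1.96 / √(1 − (d/2)² / p(1−p)))], with p(1−p) = 0.2356

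- d = 0.10: 0.0025/0.2356 = 0.0106; 1.96/√0.9894 = 1.970; size 4.9%
- d = 0.20: 0.0100/0.2356 = 0.0424; 1.96/√0.9576 = 2.003; size 4.5%
- d = 0.30: 0.0225/0.2356 = 0.0955; 1.96/√0.9045 = 2.061; size 3.9%

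**4. Simulation.** 150 versus 150, average cure 62% versus 78%, common odds ratio, at least 600,000 trials per setting. CMH is run without continuity correction; its size is 4.9-5.0% throughout. Figures are rounded to 0.1.

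| Age gap | Arms balanced within age: chi-squared size | Power, chi-squared / CMH | Gain | Age as quota only: chi-squared size | Power, chi-squared / CMH | Gain |
|---|---|---|---|---|---|---|
| 0 | 5.0% | 86.2 / 86.2 | 0 | 5.0% | 86.2 / 86.1 | −0.2 |
| 10 | 4.9% | 86.3 / 86.5 | 0.2 | 5.0% | 86.2 / 86.4 | 0.1-0.2 |
| 20 | 4.5% | 86.6 / 87.3 | 0.7 | 5.0% | 86.2 / 87.2 | 1.0 |
| 30 | 3.9% | 87.2 / 88.9 | 1.7 | 5.0% | 86.2 / 88.8 | 2.6 |

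The zero-gap loss is 86.23 − 86.06 = 0.17 before rounding.

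**5. Sensitivity to the model.** With a constant 16-point risk difference instead of a common odds ratio, the gains at 20 and 30 points are 1.0 and 2.3 (balanced) and 1.5 and 3.5 (quota). The size of the chi-squared at 150 versus 74, close to the fluocinolone comparison, is nearly the same as at 150 versus 150. Power for that comparison cannot be computed from the documents.

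**The case against.** The other side has a good case, and much of it stands.

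- **The planned test is valid.** A Pearson chi-squared on two proportions needs no stratification. Any departure from 5% is downward, so a positive result is not put in doubt.
- **A reader might infer that the primary test does run below 5%.** The documents do not support that. It needs blocking within age group, which Protocol 5.5 does not state, and an age effect on cure, which is reported nowhere. The stated purpose, representation and not statistics, also fits a simple enrolment quota, and then the size is 5.0%. Even with blocking, the primary set is the subset positive for P. aeruginosa or S. aureus. Balance there would be looser than the exact balance simulated, and the conservatism smaller.
- **The gain is small.** It is at most about 1 point of power up to a 20-point age gap under a common odds ratio, and planned power is already exceeded.
- **The age-stratified result will be reported anyway** under SAP 4.7.1.4. The proposal only changes which test is primary.
- **Two confirmatory endpoints need not share strata.** The pain diary uses age-specific scales, which might justify stratifying only that endpoint. However, the scales change at 7 and 13 years, not at 18, and the plan does not offer this reason.

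What the objection does not remove is the power argument. It depends only on whether age predicts cure, not on how the IWRS was built or why age was stratified. Nor does it identify a material drawback of the change.

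**Conclusion.** This is a cheap improvement and not an error. The unstratified chi-squared is valid. It gives up about 0.1-0.2, 0.7-1.0 and 1.7-2.6 points of power at age gaps in cure of 10, 20 and 30 points; the ranges cover arms balanced within age and age as a quota only. These figures assume 150 per arm, a 50:50 age split, 62% versus 78% and a common odds ratio. The age gap itself is an assumption; with none, there is nothing to gain. A true size below 5% needs the further condition of blocking within age group and should not be stated as fact. Power against ciprofloxacin stays above 80% in every setting examined.

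The firmest textual defect nearby needs no assumption: the synopsis and the body of the protocol name different tests for the primary endpoint.

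**What to change.** 1. In SAP 4.7.1 and 4.7.2 and Protocol 10.1.10.1, make the primary comparison of the combination with each component a CMH test stratified on the enrolment age group (under 18, 18 and over). Report a Mantel-Haenszel stratum-weighted risk difference with 95% CI.
2. Keep the unstratified chi-squared as a pre-specified sensitivity analysis.
3. State in Protocol 5.5 and the SAP whether the IWRS blocks run within age group.
4. Bring the synopsis into line with the chosen test.
5. Tidy the dependent text. SAP 4.7.3 refers several secondary endpoints to the chi-squared test of the primary endpoint, and the small-count fallback in SAP 4.7.2 is written for an unstratified table.

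**Cost.** Wording before database lock, and possibly a protocol amendment with IRB/IEC approval under Protocol 11.4. No new data are needed, and the CMH by age group is already planned. If age does not matter and was only a quota, the stratified test loses at most about 0.2 points of power.

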## 5. STUDY POPULATION

### 5.1 Inclusion Criteria

1. Male or female, at least 6 months of age;
2. Patients with diagnosis of uncomplicated acute diffuse otitis externa of less than 21 days (3 weeks) duration, with a total symptom score of at least 5 as defined under Efficacy Parameters, in at least 1 ear. The individual symptom scores, as defined in Sections 7.1.1.1, 7.1.1.3, and 7.1.1.4, must be:
  - Otalgia: at least 2 (moderate or severe);
  - Edema: at least 2 (moderate or severe);
  - Otorrhea: at least 1 (mild, moderate or severe), with sufficient quantity of otorrhea to allow culture.
3. Patients with Brighton grading of II or III in at least 1 ear, as defined in Appendix 2.
4. Patients with otorrhea of sufficient volume for sampling for microbiological culture (sample must be taken at baseline visit prior to the first study dose).
5. Willingness to refrain from swimming through end of the study.
6. For adult patients, ability to understand and provide written informed consent  
For pediatric patients, signed informed consent from patient's legally authorized representative; also, if the patient is capable of providing assent, signed assent from the patient as applicable according to local regulations.
7. Females who are not pregnant, not lactating and are not planning a pregnancy. All females of childbearing potential (those who are not premenstrual, not postmenopausal or not surgically sterile) will be able to participate only if they have a negative urine pregnancy test prior to randomization, and if they agree to use adequate birth control methods to prevent pregnancy throughout the study.  
Adequate birth control methods included topical, hormonal-oral, implantable or injectable contraceptives; mechanical-spermicide in conjunction with a barrier such as condom or diaphragm; intrauterine device (IUD); or surgical sterilization of partner (must be  $\geq$  6 months post vasectomy). For non-sexually active females, abstinence was regarded as an adequate method of birth control; however, if the patient became sexually active during the study, she must have agreed to use adequate birth control methods as defined above for the remainder of the study.

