#### **7.1.3 Therapeutic response (Overall Clinical Outcome + Microbiological Outcome)**

1. Therapeutic cure: TSSS (otalgia+edema+otorrhea) of “0” and bacteriological response eradication or presumed eradication.
2. Therapeutic failure:
  - Positive culture for pathogen or,
  - negative culture or presumed eradication with TSSS  
(otalgia+edema+otorrhea)>0

Overall Clinical Outcome + Microbiological Outcome will be determined for each patient for Visit 3 and at Visit 4 after microbiological culture results are made available to the Sponsor or designee.

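### The primary chi-squared test of therapeutic cure is valid, but it may forgo some power because it leaves out the Visit 1 total signs/symptoms score (TSSS)

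*SAP*

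**What the plan says.** **Test.** SAP 4.7.1 sets two null hypotheses, combination versus ciprofloxacin and combination versus fluocinolone, each at two-sided 5%. SAP 4.7.2 tests them with a Pearson's "Chi Squared test for independence will be used to test the hypotheses states in Section 4.7.1 that there is no difference", with Fisher's exact test as fallback. Protocol 10.1.10.1 agrees: "The proportion of patients with a therapeutic cure will be compared between the treatment groups by using a chi-squared test". Neither names a covariate or a stratum. The protocol synopsis instead names an age-stratified log-rank test for cure. That is a separate inconsistency, and it leaves TSSS out as well.

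**Endpoint.** Protocol 7.1.3 defines therapeutic cure as "TSSS (otalgia+edema+otorrhea) of" zero together with eradication or presumed eradication.

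**Baseline score.** Protocol 5.1 admits patients "with a total symptom score of at least 5 as defined under Efficacy Parameters, in at least 1 ear", with minima of 2 for otalgia, 2 for edema and 1 for otorrhea. Each item is scored 0 to 3, so an eligible ear scores from 5 (2+2+1) to 9 (3+3+3).

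**Stratified analyses.** SAP 4.7.1.4 states: "For the primary endpoint, the Cochran-Mantel-Haenszel (CMH) test will be used, stratifying on subgroup". The subgroups are age and ear wick placement, with type of concomitant medication added if needed. No analysis of the primary endpoint uses baseline TSSS.

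**Sizing.** SAP 4.10: "Assuming a two-sided significance level of 5%, and a statistical power of 80%, the required number of patients in each group would be 150". The rates are 62% on ciprofloxacin and, because the "combination will increase it by a relative 25%, which would represent a therapeutic cure rate of 78" per cent, 77.5% before rounding on the combination.

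**The concern.** Visit 1 TSSS is the baseline measurement of the clinical half of the primary endpoint. An ear that starts at 9 has more to clear by Day 8 to 10 than one that starts at 5, so the score plausibly predicts cure. If it does, the unadjusted test leaves that variation in the error term. Randomization is stratified on age only (protocol 5.5), so neither design nor analysis allows for chance imbalance in severity. Both comparisons must be significant, so power given up in either one lowers the chance of overall success. The stake is efficiency alone: type I error is controlled either way.

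**Working it through.** **Step 1. Reproduce the plan's figure.** Inputs from SAP 4.10: p1 = 0.62, p2 = 0.62 × 1.25 = 0.775, two-sided 5%, power 80%. The difference is d = 0.155 and the mean rate is 0.6975.

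- Without continuity correction: n = [1.960 × √(2 × 0.6975 × 0.3025) + 0.842 × √(0.62 × 0.38 + 0.775 × 0.225)]² / 0.155² = 136.7, so 137.
- With continuity correction: (136.7/4) × [1 + √(1 + 4/(136.7 × 0.155))]² = 149.3, so 150.

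The stated 150 per group is reproduced.

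**Step 2. Power of the planned test.** The Pearson test is written without a continuity correction. At 150 per arm:

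- 62% vs 77.5%: Φ[(0.155 − 1.960 × √(0.4220/150)) / √(0.4100/150)] = Φ(0.976) = 83.6%.
- 62% vs 78%: Φ[(0.160 − 1.960 × √(0.4200/150)) / √(0.4072/150)] = Φ(1.080) = 86.0%.

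**Step 3. Formula for adjustment.** If baseline TSSS has correlation r with cure, adjustment multiplies the variance by about (1 − r²), which is the same as n/(1 − r²) patients per arm. The documents give no r, so the range is an assumption.

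| \|r\| | Effective n | Power, 77.5% | Power, 78% |
|---|---|---|---|
| 0 | 150.0 | 83.6% | 86.0% |
| 0.1 | 151.5 | 83.9% | 86.3% |
| 0.2 | 156.2 | 85.0% | 87.4% |
| 0.3 | 164.8 | 86.9% | 89.0% |
| 0.4 | 178.6 | 89.4% | 91.3% |

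**Step 4. Simulate the actual test.** The formula ignores the cost of strata and takes one r for both arms, so it flatters the gain. CMH with strata 5, 6, 7 and 8-9 was therefore simulated against Pearson chi-squared. There were 20,000 trials per setting and 150 per arm. TSSS shares at 5 to 9 were assumed to be 20/25/25/20/10%. Cure depended on TSSS through a logistic model, with the overall rates held at 62% and 77.5% or 78%.

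| Odds ratio per TSSS point | \|r\|, ciprofloxacin arm | Change in power, points |
|---|---|---|
| 1 | 0 | -0.3 to -0.5 |
| 1.25 | about 0.14 | 0 to +0.4 |
| 1.5 | about 0.24 | about +1 to +1.5 |
| 2 | about 0.38 | about +4 |
| 2.5 | about 0.47 | about +6 |

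Type I error of the stratified test stayed close to 5% (4.9 to 5.1%).

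**Step 5. Other TSSS distributions.** Three other assumed distributions, with five separate score levels, gave -0.5 to -0.8 points at an odds ratio of 1 and +2.7 to +5.3 at 2. Using five levels costs slightly more than four when TSSS is not prognostic.

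**Step 6. Fluocinolone comparison.** SAP 4.10 plans 75 patients and states no cure rate. At an assumed 62%, 75 versus 150 gives 68.2% power against 77.5% (71.1% against 78%). At an assumed 50%, power against 78% is about 98.8%, with almost nothing left to gain. The effect of adjustment here cannot be derived from the documents.

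**The case against.** The strongest reply is that nothing is broken. The chi-squared test controls type I error, and randomization balances severity on average. At 150 per arm the test exceeds its 80% target (83.6 to 86.0%). The gain rests on a correlation that the plan does not supply, and two features hold it down: entry criteria confine TSSS to 5-9, and cure also needs a bacteriological response. All of this stands.

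The spare power is less secure than it looks. The 150 is counted in the MITT population, while the primary test runs in MITT-PA/SA, a subset. If that subset gave 120 per arm (an assumption), unadjusted power at 77.5% would be 74.6%. By the formula, adjustment would bring it to 78.6% at |r| = 0.3 and 81.7% at 0.4.

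A reader might go further and infer that power is certainly being lost, or assume a correlation of 0.5 and read a gain of 8 to 9 points from the formula. The documents support neither. Even |r| of about 0.47 needs an odds ratio of 2.5 per point, so that ciprofloxacin-arm cure falls from 90% at TSSS 5 to 19% at TSSS 9. An odds ratio of 2 already implies 86% falling to 27%. Nothing in the plan points to gradients this steep.

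A practical objection also stands. MITT-PA/SA is not limited to patients who met the entry criteria, and protocol 10.1.10.2 allows pain to be recorded as not assessable. Strata defined only for scores of 5 to 9 would leave some patients unplaced, and merging decided at the blinded review would bring discretion into a confirmatory test.

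**Conclusion.** The concern holds as a possible, inexpensive gain in efficiency. The planned test is valid and the stated sample size is not wrong because of it. For combination versus ciprofloxacin, stratifying on baseline TSSS is close to neutral if the score predicts cure weakly (odds ratio up to about 1.25 per point). It is worth about 1 to 1.5 points at 1.5 and about 4 points at 2. If TSSS does not predict cure, it costs up to about 0.5 points. These figures assume 150 per arm in the analysed population, the plan's cure rates, a logistic gradient and the assumed TSSS shares. Whether the fluocinolone comparison would gain is unknown.

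**What to change.** In SAP 4.7.1 and 4.7.2 and protocol 10.1.10.1, for each of the two confirmatory comparisons:

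- Make the primary test a CMH test stratified on Visit 1 TSSS of the evaluable ear.
- Fix the strata in advance so that every MITT-PA/SA patient has one: either 5 or below (including missing), 6, 7 and 8-9; or the coarser 6 or below (including any score below 5 or missing), 7 and 8-9.
- Write into the SAP a numerical rule for sparse strata: a minimum count per arm, and which neighbour a stratum below it joins. Leave nothing to judgement at the data review.
- Report the Mantel-Haenszel common risk difference with its 95% CI.
- Keep the unadjusted chi-squared, with its Fisher fallback, as a sensitivity analysis.

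The cost is wording and a few lines of code. No data, visits or patients are added, and the SAP already uses CMH for subgroups. The downsides are the possible loss of up to about 0.5 power points and thin strata against the 75-patient fluocinolone arm, where the coarser strata may serve better. SAP 4.11 requires changes to be final before database lock, and the adjustment is credible only if it is prespecified.
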